12 DATA REPORTING / REGULATORY REQUIREMENTS

Adverse event lists, guidelines, and instructions for AE reporting can be found in Section 7 (Adverse Events: List and Reporting Requirements).

12.1 Data reporting

12.1.1 On-Study Data Submission Schedule

Pre-treatment, on-study and off-treatment data, as well as subject response data are to be recorded in the electronic data collection screens using the PBTC RDC database. See the Required Data and Timetable for Submission form located on the PBTC-039 protocol and resources webpage for the schedule. For assistance, contact the PBTC Protocol Coordinator, listed on the protocol title page. An optional roadmap is located on the PBTC-039 protocol and resources webpage.

12.1.2 Method

This study will be monitored by the Clinical Data Update System (CDUS) Version 3.0. A protocol and subject-specific CDUS "Abbreviated" data set will be submitted electronically to CTEP on a quarterly basis, either by FTP burst of data or via the CDS web application. Reports are due January 31, April 30, July 31, and October 31. Instructions for submitting data using the CDUS can be found on the CTEP website (http://ctep.cancer.gov/reporting/cdus.html).

12.2 CTEP Multicenter Guidelines

12.3 Participant and Data Confidentiality

Participant confidentiality is strictly held in trust by the participating investigators, and their staff. This confidentiality is extended to cover testing of biological samples and genetic tests in addition to the clinical information relating to participants. Therefore, the study protocol, documentation, data and all other information generated will be held in strict confidence. No information concerning the study and the data will be released to an unauthorized third party without the prior written approval of the Pediatric Brain Tumor Consortium (PBTC).

The PBTC protocol coordinators, other authorized representatives of the sponsor, regulatory representatives, PBTC auditors, representatives of the IRB or the pharmaceutical collaborator supplying study product may inspect all documents and records required to be maintained by the investigator, including but not limited to, medical records (office, clinic, or hospital) and pharmacy records for the participants in this study. The clinical study site will permit access to such records.

Source documents which are the original records of clinical findings, observations or activities in a clinical trial are to be maintained at each participating site. Sites must upload all source documentation which supports the eligibility of the participant to the PBTC. In the event the patient experiences unexpected events, additional source documentation may be requested to complete the event review. These documents may include but are not limited to, hospital records, clinical and office charts, laboratory notes, memoranda and radiographic images.

Study participant study related data, which is for purposes of statistical analysis and scientific reporting will be submitted to the Pediatric Brain Tumor Consortium. This will not include the participant's contact or identifying information. Rather, research participants and their research data will be identified by a unique study identification number assigned at the time of screening or registration. The study participant's contact information will be securely stored at each clinical site for internal use during the study. At the end of the study, all records will continue to be kept in a secure location for as long a period as dictated by local IRB and institutional regulations.

The study data entry and study management systems used by clinical sites and by the PBTC will be secured and password protected. At the end of the study, all study data is maintained on a secure server.

After the study is completed, the data collected will be maintained on a server and may be used by other investigators, including those outside the study. With the participant's approval and as approved by local IRBs, biological samples labeled only with the participant's protocol specific identification number will be stored at the PBTC Central Review and Biorepository and could be made available to other investigators for future unspecified research. Investigators conducting future studies will not have access to the key for stored data collected while the participant is on study. Clinical data will be de-identified before it is shared with other investigators.

If the participant agrees to submit a repository sample, those samples contain genetic information that may be used for research related to brain tumors and their treatment. They may also be used to develop tests/assays to improve diagnosis and treatment of these diseases in the future.

Genetic research may consist of the analysis of one or more genes or the analysis of genetic markers throughout the genome.

13 STATISTICAL CONSIDERATIONS

13.1 Primary Endpoints

Stratum 1: Rate of disease stabilization for 1 year (i.e. 9 courses of treatment).

Stratum 2: Sustained Objective Response (PR+CR) rate in the cystic and/or soft tissue component observed during the first year of treatment (i.e. 9 courses of treatment). Response must be sustained for 3 months.

13.2 Secondary Endpoints

Stratum 1: Sustained objective response rate and progression free survival

Stratum 2: Progression free survival

13.3 Sample Size/Accrual Rate

Stratum 1:

The design will be based on proportion of patients who complete 9 courses of treatment (approximately 1-Year) without an event (PD or death for any reason). Even though the primary outcome variable for this stratum has a long duration, since the PBTC (or the COG) has no historical data available on which we could base a design, we chose to use a binomial endpoint. While the use of a binomial outcome variable results in some loss of information, it allows us to avoid making distributional assumptions which cannot be checked due to unavailability of historical data. Patients in stratum 1 will be enrolled at the time of progression.

A summary of the proposed design for this stratum are provided in the table below. For patients who have never received radiation, >50% 1-year disease stabilization rate is felt to be the minimal acceptable threshold, since radiation can achieve high rates of disease control for at least a year with reported long term disease control rates of 75-90% 13-15. In this study we are targeting 75% as the desirable rate for 1-year disease stabilization. More specifically, PEGINTERFERON ALFA-2B will be deemed not worthy of further investigation in this patient population, if the true 1-year disease stabilization rate is less than 50% and the design will have 90% statistical power for a true disease stabilization rate of 75%. These parameter settings coupled with type I error rate set at 10% lead to a sample size of 28 eligible and evaluable patients based on a 1-sample 1-sided exact binomial design. If 18 or more patients experience disease stabilization that lasts for at least 1 year, then we will conclude that PEGINTERFERON ALFA-2B is sufficiently active in this disease to warrant recommendation for continued investigation. We will conduct an interim analysis for futility once 12 patients have been enrolled and followed for 1 year (accrual will not be stopped for interim analysis). If we observe 6 or fewer patients who complete 1-year without an event among the 1st twelve patients treated, then we will stop accrual early for lack of evidence of adequate activity. If the true 1-year disease stabilization rate is 50%, there is a 61.6% chance that the trial will stop early for lack of efficacy. On the other hand, if the true 1-year disease stabilization rate is 75%, the probability that we will

stop early is 5.0%. The attained significance level and power of this design are 0.082 and 0.902, respectively.

Table 3

One-Sample Group Sequential Exact Binomial Design for Efficacy Monitoring

Efficacy: Unacceptable $\leq 50\%$, Desirable $\geq 75\%$ ($\alpha = \beta = 0.1$)

| | n | Efficacy |
|---------|----|--------------------------------------|
| Stage 1 | 12 | Stop if number of "successes" ≤ 6 |
| Final | 28 | Reject if number of "successes" ≤ 17 |

Accrual Duration:

Based on our informal survey prior to the initiation of this study, PBTC sites estimated that they each saw 1-2 patients per year who would be eligible to enroll on this stratum. Hence we originally estimated that it will take approximately 2.5-3 years to complete accrual taking into account the long outcome assessment window which is our main reason for not considering a Simon-type design where accrual would have to be suspended at the time of the interim analysis. As of amendment 3, the actual accrual rate proved to be substantially slower than this estimate with approximately 4 patients per year, taking into account the initial period when sites put the protocol through their IRBs etc. So based on this revised accrual estimate, we expect to complete accrual to this stratum in 5-6 years. The timing of the interim analysis is difficult to estimate but we expect that it will occur approximately 3.0-3.5 years after initiating accrual.

Stratum 2:

Objective response (CR+PR) rate observed during the first year of treatment (more specifically during the first 9 courses) is the primary endpoint for this stratum. In order to count towards the success criteria, objective responses observed during the first year must be sustained for 3 months. Simon's optimal two-stage design will be employed in this stratum, where accrual will stop, i.e. the trial will terminate early if evidence accumulates that the efficacy is lower than the specified acceptable levels. For patients who have failed radiation, >10% response rate will be the minimal acceptable threshold for response, but > 35% will be the threshold to establish efficacy. More specifically PEGINTERFERON ALFA-2B will be deemed not worthy of further investigation in this patient population if the true sustained objective response (CR+PR) rate during the first year of treatment is less than 10% and the design will have 90% statistical power for a true response rate of 35%. These parameter settings coupled with type I and II error rates set at 10% lead to a sample size of 19 eligible and evaluable patients based on a Simon's optimal design. Eleven (11) patients will be accrued in the first stage and if one (1) or fewer sustained objective responses are observed among the first 11 patients during their 1st year of treatment, the stratum will be closed to accrual and we will conclude that PEGINTERFERON ALFA-2B does not merit continued investigation in this disease due to lack of efficacy. Otherwise accrual will continue until 19 evaluable patients have been treated and assessed for objective response and toxicity. If four or more (≥ 4) patients experience sustained objective responses (CR+PR), then

we will conclude that PEGINTERFERON ALFA-2B is sufficiently active in this disease to warrant recommendation for continued investigation. With this design if the true response rate is 10%, the probability that the trial will stop early is 70%. However, if the 'true' response probability is 35%, then there is a 6% chance that the trial will terminate in stage 1. While it is possible that the study will be closed to accrual for an extended period (up to 15 months) to assess outcome at the time of the interim analysis, considering the very low efficacy thresholds established for this stratum, and the relatively slow expected accrual rate, it is unlikely that this will be the case. If we reach 10 patients and we only have 1 response, it would be prudent to suspend accrual until the outcome for the last patient is available in order to avoid exposing additional patients to an ineffective agent.

Table 4

Simon's Optimal Two-Stage Design for Efficacy Monitoring Efficacy: Unacceptable $\leq 10\%$, Acceptable $\geq 35\%$ ($\alpha = \beta = 0.1$)

| | n | Efficacy |
|---------|----|-------------------------------------|
| Stage 1 | 11 | Stop if number of "successes" ≤ 1 |
| Final | 19 | Reject if number of "successes" ≤ 3 |

Accrual Duration:

During the planning stages of the trial, the PBTC sites estimated similar numbers (perhaps slightly lower than Stratum I) for accrual in this stratum (i.e., 1-2 patients per year/site). Based on this information, we estimated that it will take Approximately 1.5 years to reach the interim analysis sample size and approximately 2.5 years to finish accrual (not including any prolonged closure at the time of the interim analysis). As of amendment 3, based on the slower than expected accrual rate, we are revising the accrual estimates to 6 patients per year and thus we estimate that the trial will complete accrual in 3-4 years with an expected interim analysis to be performed approximately 2 years after initiating accrual.

Combined accrual for Strata I and II:

This is the first PBTC study for this patient population and therefore we do not have specific accrual data for patients with craniopharyngiomas. Thus the estimates in the table below are based on enrollment information from recent PBTC studies for other brain tumors. The maximum total planned accrual to this trial is 47 eligible and evaluable patients. Taking into account the possibility of some patients being declared ineligible or inevaluable, we estimate that we will enroll no more than 52 patients on this trial.

Table 5

| TARGETED/PLANNED ENROLLMENT: Number of Subjects | | | | |
|---|------------|-------|-------|--|
| Ethnia Catagomy | Sex/Gender | | | |
| Ethnic Category | Females | Males | Total | |
| Hispanic or Latino | 3 | 4 | 7 | |

| Non-Hispanic | 23 | 22 | 45 |
|---|----|----|----|
| Ethnic Category: Total of All Subjects | 26 | 26 | 52 |
| Racial Categories | | | |
| American Indian/Alaskan Native | 0 | 0 | 0 |
| Asian | 1 | 1 | 2 |
| Native Hawaiian or other Pacific Islander | 0 | 0 | 0 |
| Black or African American | 3 | 4 | 7 |
| White | 20 | 19 | 39 |
| More Than One Race | 2 | 2 | 4 |
| Racial Categories: Total of All Subjects | 26 | 26 | 52 |

Analysis Plan:

At the time of reporting, exact confidence interval estimates will be provided for the true, unknown rates of objective response for each stratum separately and 1-year disease stabilization rate for stratum 1. In addition to the usual estimates of response, we will estimate the confirmed sustained objective response rate (CR+PR) observed during treatment by cumulative incidence functions for each stratum. This provides not only an overall estimate of the objective response rate, but also an estimate of the timing of responses as a function of number of months of treatment. In this analysis, patients who are removed from treatment (due to disease progression, death or unacceptable toxicity) will be considered as having had a competing event. Patients who have stable disease and acceptable toxicity as of their last date of treatment will be censored on that date in the analysis. Note that this secondary analysis will include sustained objective responses that may be observed beyond the first year of treatment.

Kaplan-Meier estimates of distributions of PFS for all eligible patients who receive at least one dose of PI will be provided separately for each stratum. PFS will be measured from the date of initial treatment to the earliest date of disease progression, second malignancy or death for any reason for patients who fail; and to the date of last contact for patients who remain at risk for failure.

Both for objective response assessments as well as PFS calculations, the assessments made at the treating site will be used. Any discrepancies between the treating sites' assessments and the central review will be recorded and described.

Toxicity data will be summarized via frequency tables both for episodes and for number of patients separately for each stratum. We will also tabulate the data related to dose reductions and treatment discontinuation due to toxicity.

Analysis Plan for Central Imaging Review:

All imaging studies obtained during the first year of treatment in Stratum I as well as all scans with the smallest disease measurement recorded since the start of protocol and scans documenting objective response or progressive disease in both strata will be centrally reviewed at the end of the study. We will summarize any discordance between site's assessment and the central review across patients within a stratum as well as on a per patient basis taking into account the longitudinal data that will be available especially in Stratum I. Specific attention will

be given to PD assessment as we anticipate that there will be cases where PD criteria will be satisfied based on protocol definition but not by MacDonald criteria and vice-versa.

Analysis Plan for the WNT pathway activation data:

We will summarize the frequency of nuclear beta-catenin by IHC in FFPE tumor sections. We will also explore associations between presence of nuclear beta-catenin and outcome. Separately in each stratum, if we observe 10 or more responses among patients from whom biology data are available, we will use exploratory logistic regression models to look for associations between biological markers and response. Similarly, if we observe 10 or more progressions among patients from whom biology data are available in a stratum, we will explore associations between biological markers and PFS. Otherwise association with response and PFS will be summarized descriptively.

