5.3 Duration of Therapy

In the absence of treatment delays due to adverse event(s), treatment may continue for up to 18 courses:

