5.3.2 Off Treatment Criteria

At the discontinuation of treatment, the "Off Treatment Date" is to be recorded in the eCRF and is to be consistent with the reason given for going off treatment. The "Last Treatment Date" is defined as the last date that the patient received protocol based therapy. Date of "off treatment" must be the greatest of the date of last treatment, date of procedure, date of patient assessment, notification of patient/family decision, or decision made by the physician that resulted in the patient being taken off protocol treatment. The reason for discontinuation of treatment must be documented by the attending investigator in the medical record and recorded in the eCRF.

- Disease progression as defined in Section 11.1.3
- Development of a medical or psychiatric illness that in the investigator's judgment renders the patient incapable of further therapy on this protocol.
- Unacceptable toxicity as outlined in sections 6.
- Patient, parent or legal guardian refuses further treatment on this protocol
- Pregnancy or breastfeeding
- Subject is unable to complete the study evaluations/visits
- Patients who develop significant depression and/or suicidal ideations will be taken off treatment.

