13.4.1 Definition of Evaluable Patients

In both strata, all patients who receive at least 1 dose of PEGINTERFERON ALFA-2B will be considered evaluable for the purposes of assessing the primary objectives of this trial.

In both strata, patients who withdraw, are lost to follow-up, and/or are removed from treatment and who fail to be evaluated for the primary outcome will be counted as failures.

REFERENCES

- **2.** Rubinstein LJ RD. *Pathology of Tumours of the Nervous System.* 5 ed. Baltimore: Williams & Wilkie; 1990.

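### In the secondary cumulative incidence analysis of response, patients with stable disease who stop treatment early are censored rather than counted as competing events, which can overstate the on-treatment response rate

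*Combined protocol and SAP*

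**What the plan says.** The Analysis Plan in section 13.3 states: "we will estimate the confirmed sustained objective response rate (CR+PR) observed during treatment by cumulative incidence functions for each stratum". The curve is meant to give an overall response estimate and also "an estimate of the timing of responses as a function of number of months of treatment". It is not limited to year 1, because "this secondary analysis will include sustained objective responses that may be observed beyond the first year of treatment". Section 5.3 sets the horizon: "treatment may continue for up to 18 courses", which at six weeks per course is 108 weeks.

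Two rules govern patients without a response. First, "patients who are removed from treatment (due to disease progression, death or unacceptable toxicity) will be considered as having had a competing event". Second, "Patients who have stable disease and acceptable toxicity as of their last date of treatment will be censored on that date".

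Section 5.3.2 allows treatment to stop for reasons outside that competing-event list. One is "Patient, parent or legal guardian refuses further treatment on this protocol". Others are inability to complete study visits, pregnancy or breastfeeding, and a medical or psychiatric illness that rules out further therapy.

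For the primary outcome, section 13.4.1 takes another line: "patients who withdraw, are lost to follow-up, and/or are removed from treatment", if not evaluated for that outcome, are counted as failures.

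**The concern.** The quantity is response while on treatment, on a time scale of months of treatment. A patient with stable disease who refuses further drug at week 20 cannot respond on treatment after week 20, just as a patient stopped for toxicity at week 20 cannot. The plan treats the second as a competing event and censors the first. Censoring assumes that the patient remains able to respond and would have done so at the rate of those who stayed on drug. That is an assumption about a hypothetical continuation of treatment. It is not what the plan says it estimates, and it does not fit with making toxicity stops competing events.

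What is at stake is the reading of a secondary curve. In stratum 2 the same patient can be a failure in the primary response rate and a censored potential responder in the curve. Because the curve also takes in responses after year 1, some of any gap between the two could be put down to late responses when it comes from the censoring.

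**Working it through.** **Plan's own figure.** The documents give neither a number for this curve nor a rate of early stable exits, so there is nothing to reproduce. All event rates and event times below are assumptions. Only the 108-week horizon (section 5.3), the sample sizes of 19 and 28 (section 13.3) and the two rules come from the documents.

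**Check 1: constant hazards.** Let *r* be the yearly hazard of sustained response, *c* that of progression, death or toxicity removal, and *w* that of early stable exit, with *T* = 108/52 = 2.077 years.

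- Exits censored, as written: CIF = r/(r+c) × [1 − exp(−(r+c)T)]
- Exits as competing events: CIF = r/(r+c+w) × [1 − exp(−(r+c+w)T)]

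For r = 0.2, c = 0.35, w = 0.1:

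- Censored: 0.2/0.55 × [1 − exp(−1.142)] = 24.8%
- Competing: 0.2/0.65 × [1 − exp(−1.350)] = 22.8%

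The full set, with c = 0.35 throughout:

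| r | w | Patients leaving early and stable | Censored | Competing | Gap (points) |
|---|---|---|---|---|---|
| 0.2 | 0.02 | 2.4% | 24.76% | 24.35% | 0.41 |
| 0.3 | 0.02 | 2.2% | 34.19% | 33.64% | 0.55 |
| 0.2 | 0.05 | 5.9% | 24.76% | 23.75% | 1.01 |
| 0.3 | 0.05 | 5.5% | 34.19% | 32.84% | 1.35 |
| 0.2 | 0.1 | 11.4% | 24.76% | 22.79% | 1.97 |
| 0.2 | 0.2 | 21.1% | 24.76% | 21.05% | 3.71 |
| 0.3 | 0.2 | 19.5% | 34.19% | 29.25% | 4.93 |

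**Check 2: a finite sample the size of stratum 2.** Assume 19 patients, with:

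- sustained responses at weeks 24, 36, 48 and 72
- progression or toxicity exits at weeks 12, 24, 36 and 54
- early stable exits added in turn at weeks 8, 14, 20, 30, 40 and 50
- everyone else completing 108 weeks

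The Aalen-Johansen estimate with the exits as competing events ends at 4/19 = 21.1%, however many exits there are. With the exits censored:

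- One exit, at week 8, before any event: 18 patients remain at risk and the curve ends at 4/18 = 22.2%.
- Two exits: after the week 12 progression 17/18 are event-free, and after the week 14 exit 16 remain at risk. Each response then adds (17/18)/16 = 0.0590, and four give 23.6%.
- Three to six exits: 25.2%, 26.8%, 28.3% and 29.4%.

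No extra response has occurred in any of these cases. For a stratum 1-sized sample (n = 28, 5 responses, 6 competing exits), 5/28 = 17.9% becomes 18.5% to 22.1% with one to six early exits.

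**Where the gap vanishes.** With no early stable exits the two versions agree. If four stable patients leave at week 80, after the last response at week 72, the stratum 2 curve still ends at 21.1%. Censoring at the end of 18 courses also adds nothing at the 108-week horizon.

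**The case against.** A fair opponent would make five points.

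1. **The affected group is narrow.** Censoring is right for patients still on drug at analysis and harmless for 18-course completers. Some section 5.3.2 stops may already count as toxicity: depression and suicidal thoughts are listed drug effects in section 7.1, so a stop for them can be classed as unacceptable toxicity. This stands. It would be too broad to say that every exit other than progression, death or toxicity is censored. The residue is refusal, missed visits, pregnancy or breastfeeding, and illness not classed as toxicity.
2. **The overstatement is conditional.** This stands. A reader might infer that the curve is bound to exceed the primary rate because of the censoring. The documents do not support that, since they give no exit rate and the gap can be zero.
3. **It is small against precision.** One patient is 1/19 = 5.3 points in stratum 2 and 1/28 = 3.6 points in stratum 1, and the exact 95% interval for 4/19 runs from 6.1% to 45.6%. This stands as to size, but the error is systematic and costs almost nothing to remove.
4. **Readers are partly protected.** Exact intervals for response are reported as well, and the curve can be read at 9 courses. There, with w of 0.1 to 0.2, the gap is only 0.7 to 2.0 points. Responses after 9 courses add 24.8 − 15.8 = 8.9 points (r = 0.2) or 34.2 − 22.7 = 11.5 points (r = 0.3), so most of a visible rise would be genuine. The comparison with a primary response rate also arises only in stratum 2, because stratum 1's primary endpoint is stabilization.
5. **Section 13.4.1 is not contradicted.** A reader might see a conflict between its failure rule and the censoring rule. Its wording covers the primary outcome only, so a secondary curve may follow another rule. The contrast shows a difference in handling and no more.

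None of this rescues the rule for the quantity the plan names. Censoring early stable leavers would suit a hypothetical rate of response had they stayed on drug, which the plan does not state.

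**Conclusion.** The point holds in a limited form. As written, the rule censors patients with stable disease and acceptable toxicity who stop early, although they can no longer respond during treatment. If such exits precede later responses in others, the curve is too high. The direction follows from the estimator; the size cannot be fixed from the documents. Under the assumed hazards it runs from under 1 point when about 2% leave this way to about 5 points when about 20% do. The small-sample illustration reaches 8.3 points (29.4% against 21.1%), but only with six of 19 patients leaving early.

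A reader might infer that the trial's conclusions are affected. They are not: the decision rules in section 13.3 use counts of successes, to which section 13.4.1 applies, and nothing in them depends on this curve. This is a minor correction to a secondary analysis.

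**What to change.** Replace the censoring sentence in section 13.3 with a rule of this kind: any permanent stop of protocol treatment before a response and before completion of 18 courses, for any section 5.3.2 reason, is a competing event; only patients still on treatment at data cut-off, or who complete 18 courses without a response, are censored. Once nobody remains on treatment, the end of the curve then equals responders divided by patients treated.

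The cost is one sentence. Off-treatment dates and reasons are already recorded in the eCRF under section 5.3.2, so no new data are needed. The only downside is a slightly lower reported rate if early stable exits occur.
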